### 6.2.3. Device Removal Procedure

Following completion of chemotherapy treatment, M-Trap devices will be removed under one of following scenarios, whichever occurs first:

- (1) In the event of an adverse event necessitating device removal.
- (2) After disease progression as defined by objective RECIST 1.1 and CA-125 criteria. Both criteria must be met as follows:

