#### Gynecological Cancer Intergroup criteria

- i. Patients with elevated CA-125 pretreatment and normalization of CA-125 must show evidence of CA-125 greater than, or equal to, 2 times the upper limit of the reference range on 2 occasions at least 1 week apart, or
- ii. Patients with elevated CA-125 before treatment, which never normalizes, must show evidence of CA-125 greater than, or equal to, 2 times the nadir value on 2 occasions at least 1 week apart, or
- iii. Patients with CA-125 in the reference range before treatment must show evidence of CA-125 greater than, or equal to, 2 times the upper limit of the reference range on 2 occasions at least 1 week apart.

- (3) At the final 18-month post-implantation time point.

\* Baseline is defined as the follow-up time point following completion of chemotherapy treatment.

Device removal will be performed via minimally invasive surgery (laparoscopy) following the institution's standard protocols. To remove the device, M-Trap device(s) will be located, carefully segregating the device with any captured tumor cells from the surrounding tissues. Next, a single-use specimen retrieval system (Endobag™ container) will be placed to recover the extracted M-Trap device through the 15mm trocar cannula of the laparoscopic port, maintaining the integrity of the device for histological analysis.

The laparoscopy will be completed following the institution's standard protocols. An assessment of the device removal procedure will occur at the time of explant, including ease of locating and removing the M-Trap device and the occurrence of any device- or procedural-related AEs during the removal procedure. If for some reason the device(s) cannot be explanted through laparoscopy, the surgeon should proceed using best clinical judgement, including a potential conversion to laparotomy.

Semi-quantitative scoring of disease focalization based on direct visual assessment, CT scan and ultrasound will be performed at the time of device removal, using the following scale:

Degree of Disease Focalization	Definition
I	Approximately 100% of recurrent disease contained in M-Trap devices
II	Approximately 75% of recurrent disease contained in M-Trap devices
III	Approximately 50% of recurrent disease contained in M-Trap devices
IV	Approximately 25% of recurrent disease contained in M-Trap devices
V	No obvious recurrent disease contained in M-Trap devices

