Following device removal, mark the side of the device that faced outward into the peritoneal cavity with an "X" using a surgical suture. Place each explanted device in a separate, labelled container prepared per standard institution protocol. Labels shall include institution name, protocol number (MTRAP-2016-01), study subject identification number, date of explant, and location of explant (i.e., right paracolic gutter, left paracolic gutter, liver). The hospital laboratory must follow Appendix 1 to prepare the explant for shipping to the core laboratory. After standard pathological analysis at the institution, samples shall be shipped following the institution's protocols for shipment of biological samples to the core laboratory for histology evaluation:

[name] / [name]  
 Hospital Arnau de Vilanova, Anatomia Patològica  
 [name]  
 [name]  
 [contact]  
 Email: [contact], [contact]

All patients will be followed through 18 months, regardless of whether or not the device was removed at an earlier time point.

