2.4.7. Device Removal

Descriptive statistical data will be used to draw up a recapitulation of the device removal details at the time of the removal operation.

The following data will be presented on the As-Treated population on patients number:

- Duration until device removal (days), Reason for removal, All devices removed (Yes/No), The number of devices removed if No. Duration until device removal (days) if the reason for removal is recurrence.
- The time to recurrence will be described using a Kaplan Meier curve. Patients lost to follow-up before the removal will be censored at the date of last follow-up. Patients who have removal for another reason than recurrence before the 18 months will be censored at the date of the removal.
- Disease Focalization: Disease focalization score, Modalities used for the assessment of disease focalization, If a peritoneal wash performed, were malignant cells present (Yes/No)
Disease Focalization will be also analyzed using the 3 sub-populations defined below ((1), (2), (3)), and using the populations (1) and (2) combined and overall.
- Adverse Event: New adverse event(s) occur during removal procedure (Yes/No)
- Cytology (Done with final device removal): Where ascites present (Yes/No), Were malignant cells present in the ascites (Yes/No), Was a peritoneal wash performed (Yes/No), From which area was the wash obtained if "Yes", Were malignant cells present in the peritoneal wash.

	STATISTICAL ANALYSIS PLAN	MTRAP_SAP_v2.0_FINAL redacted.docx
		MTRAP Page 14/15

- Biopsies (Done with final device removal): Biopsy location, Biopsy taken (Yes/No), Is visible tumor present (Yes/No), Is microscopic disease present (Yes/No)

If Biopsy location is Adhesive bands, abnormally scarred areas or Retroperitoneum the further details given will be described by the mean of listing.

The following data will be presented on the As-Treated population on devices number:

- Location of Device, Attachment of the device to the surrounding tissues
- Assessment of device removal: Ease of locating M-Trap device, Did the M-Trap device remain securely fixed in its original location, Ease of removing M-Trap device, Endobag used, Trocar size (mm)
- Core Lab: Device(s) sent to the core laboratory (Yes/No), the Reasons and the Location if No

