Add 1 to the score if Large bowel resection is ticked (colectomy, rectosigmoid resection).

Add 1 to the score if Diaphragm peritonectomy or Full-thickness diaphragm resection (diaphragm resection) is ticked.

Add 1 to the score if Partial hepatectomy (hepatic resection) is ticked.

- Derived criterion “freedom of device- and procedure-related major adverse events through 6 months post-implantation, including shock, cardiac arrest, myocardial infarction, pulmonary embolism, prolonged intubation, unplanned reintubation, or adverse events leading to removal of the device, including infection, seroma formation, mesh migration, bowel obstruction, adhesions, and local cancer progression through the abdominal wall at M-Trap suture sites” which is the primary endpoint will be calculated as follows:

If a MAE occurred in a patient within 6 months \pm 2W post implantation and “Does this event meet the definition of a major adverse event for the primary endpoint?” = “Yes” then “freedom of device- and procedure-related major adverse events through 6-months post-implantation” = “No” else “freedom of device- and procedure-related major adverse events through 6-months post-implantation” = “Yes”.

- Derived criterion “recurrent patients” will be defined as patients with device removal reason “Disease progression as defined by objective RECIST 1.1 and CA-125 criteria” or device removal reason “other” that indicates recurrence. Derived criteria “non-recurrent patients” are the remaining patients. CRO will send to MTrap an excel file with the list of all other reason of device removal to identify the reason that indicates “recurrence”.
- Derived criterion “time to recurrence” will equal to the date of the follow-up visit when “Device removal planned for this visit” is yes minus the procedure date.
- Derived criterion “platinum resistant, recurrent patients” will be defined as “recurrent patients” where the difference between the date of the follow-up visit when “Device removal planned for this visit” is yes and the date of the most recent chemotherapy medication treatment is less than or equal to 180 days.
- CRO will send to MTrap an excel file with the list of the concomitant medication to identify the chemotherapy medication treatment. Derived criterion “platinum sensitive, recurrent patients” will be defined as “recurrent patients” that are not “platinum resistant, recurrent patients”.

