 Table 82: Disease focalization scores of I, II or III on AT population (Type 5)
 Table 83: Disease focalization scores of I, II, III or IV on AT population (Type 5)
 Table 84: Disease focalization scores of I on AT population by recurrence status (Type 5)
 Table 85: Disease focalization scores of I or II on AT population by recurrence status (Type 5)
 Table 86: Disease focalization scores of I, II or III on AT population by recurrence status (Type 5)
 Table 87: Disease focalization scores of I, II, III or IV on AT population by recurrence status (Type 5)

Device(s) removal

Device removal information

Table 88: Duration until device removal (months) (Type 7)
 Table 89: Duration until device removal for recurrent patients (months) (Type 7)
 Table 90: Reasons for removal (Type 5)
 Table 91: All device(s) removed (Type 5)
 Table 92: Time for removal for recurrent patients – Kaplan Meier curve

Device location

Table 93: Location of removed device (Type 4)

Table 94: Attachment of removed device

Assessment of device removal

Table 95: Ease of locating M-Trap device (type 5)
 Table 96: Ease of locating M-Trap device by device location (type 5)
 Table 97: Ease of removing M-Trap device (type 5)
 Table 98: Ease of removing M-Trap device by device location (type 5)
 Table 99: Trocar size (mm) (Type 5)

	STATISTICAL ANALYSIS PLAN	MTRAP_SAP_v2.0_FINAL redacted.docx MTRAP Page 20/21
--	----------------------------------	--

Disease Focalization

Table 100: Disease focalization score (Type 5)

Table 101: Disease focalization score by recurrence status (Type 5)

Adverse Events

Table 102: New adverse event(s) occur during removal procedure (Type 5)

Cytology

Table 103: Cytology at device removal (Type 5)

Biopsy (Done with final device removal)

Table 104: Biopsy taken at final device removal (Type 4)

Table 105: Visibility of tumor present (Type 4)

Table 106: Microscopic disease present (Type 4)

Pathology analysis

Table 107: Device Length (mm) and Width (mm) (Type 7)

Table 108: Device Length (mm) and Width (mm) by location device (Type 7)

Table 109: Immunohistochemistry (Type 7)

Table 110: Immunohistochemistry by location device (Type 7)

Table 111: Tumor cell infiltration (type 7)

Table 112: Photo (Type 4)

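### The time-to-recurrence curve measures time to planned device removal: recurrence is recognised and dated only through removal, and follow-up after removal goes unused

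*SAP*

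**What the plan says.** **Event.** SAP 2.5 counts a patient as recurrent if the removal reason is progression by RECIST 1.1 and CA-125, or a "device removal reason “other” that indicates recurrence". All remaining patients are non-recurrent. Time to recurrence "will equal to the date of the follow-up visit when “Device removal planned for this visit” is yes minus the procedure date".

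**Progression rule.** Protocol 6.2.3 lists progression as one trigger for removal and says of the RECIST 1.1 and CA-125 parts: "Both criteria must be met as follows". The CA-125 part needs a repeat value, for example "2 times the nadir value on 2 occasions at least 1 week apart".

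**Censoring.** SAP 2.4.7 has two rules. Patients lost to follow-up before removal are censored at last follow-up. For the rest: "Patients who have removal for another reason than recurrence before the 18 months will be censored at the date of the removal".

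**Follow-up.** Protocol 6.2.3 states: "All patients will be followed through 18 months, regardless of whether or not the device was removed at an earlier time point". Protocol 6.4 schedules CT and CA-125 at every follow-up visit from month 3. Protocol 6.7.2 makes the exception: nothing is collected after a patient withdraws.

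**Population.** SAP 2.4.7 places the curve among the items reported on the As-Treated population. SAP 4.1 titles the only Kaplan-Meier output, Table 92, "Time for removal for recurrent patients".

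**Death.** SAP 2.4.6 gives an overall mortality rate. Neither the censoring rules nor the lost-to-follow-up definition in Protocol 6.7.1 mentions death.

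**The concern.** A reader of a time-to-recurrence curve expects the event to be the disease and the clock to stop when the disease is documented. Here both hang on a surgical decision. A recurrence without a removal is not an event, nor is one that appears after the device has been taken out for another reason, even though the visits that would show it are scheduled and recorded.

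This is the only time-to-recurrence analysis listed in the SAP. The same visit date also feeds the 180-day split into platinum-resistant and platinum-sensitive recurrence in SAP 2.5, which defines sub-populations for the performance analyses. A late date can move a patient from resistant to sensitive: three months is about 91 days, roughly half of the 180-day cut-off.

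**Working it through.** **Inputs.** The plan gives no expected value for this curve, so there is no figure to reproduce. Protocol 1.5 expects about 40% to 50% of the target population to have progressed at 12 months. From month 3 the nominal visit interval is 3 months (Protocol 6.4). Everything else below is assumed and shown as a range. Recurrence is taken as exponential, with 45% at 12 months as the middle case: λ = −ln(0.55)/12 = 0.0498 per month.

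**1. The rules applied to four hypothetical patients**

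| Course | Result under the SAP |
|---|---|
| Both criteria met at month 9, removal planned at that visit | Event at month 9; no delay |
| Both criteria met at month 9, removal planned at the month-12 visit | Event at month 12; 3 months late |
| Device out at month 7 for an adverse event, both criteria met at month 12 | Censored at month 7; the observed recurrence is never counted |
| Both criteria met, device never removed | No removal reason, so classed non-recurrent; no removal-planned visit to date from |

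**2. Late dating.** With a constant lag L, the share shown as recurrence-free at 12 months is exp(−λ(12 − L)).

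- L = 0: 0.550
- L = 0.25: 0.557
- L = 1: 0.578
- L = 2: 0.608
- L = 3: 0.639, which is 0.089 too high

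At L = 3 the rise is from 0.600 to 0.682 if 40% have progressed at 12 months, and from 0.500 to 0.595 if 50% have. The median moves by L.

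**3. Censoring at removal.** This was simulated with 200,000 patients. A share q have the device removed for another reason, uniformly between months 3 and 12, and their recurrence hazard is h times that of the others throughout. Shares recurrence-free at 18 months:

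| q | h | True | Kaplan-Meier, censored at removal | Difference |
|---|---|---|---|---|
| 5% | 1 | 0.408 | 0.408 | 0.000 |
| 5% | 2 | 0.396 | 0.401 | +0.005 |
| 30% | 2 | 0.336 | 0.369 | +0.033 |
| 5% | 0.5 | 0.418 | 0.411 | −0.007 |
| 30% | 0.5 | 0.478 | 0.437 | −0.041 |

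With equal hazards the rule loses data but causes no bias.

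**4. Death without recurrence.** Let 5%, 10% or 20% die by 12 months, at constant hazard μ. If deaths are censored, one minus Kaplan-Meier at 18 months is 0.592. The cumulative incidence, λ/(λ+μ) × (1 − exp(−18(λ+μ))), is 0.573, 0.554 and 0.516. If death counts as an event, the share free of both, exp(−18(λ+μ)), is 0.378, 0.348 and 0.292, against 0.408 with censoring. The choice matters and the plan does not make it.

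**5. Table 92 title taken literally.** By month 18 a proportion F(18) = 1 − (1 − f)^1.5 has recurred, where f is the 12-month proportion. Among those patients alone, the share still recurrence-free at 12 months is (F(18) − f)/F(18).

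| f | F(18) | All patients: share at 12 months, median | Recurrent only: share at 12 months, median |
|---|---|---|---|
| 40% | 0.535 | 0.60, 16.3 months | 0.253, 7.3 months |
| 45% | 0.592 | 0.55, 13.9 months | 0.240, 7.0 months |
| 50% | 0.646 | 0.50, 12.0 months | 0.227, 6.8 months |

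The recurrent-only curve reaches zero by construction.

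**6. Scale.** With 22 patients and no censoring, the standard error of a 12-month share of 0.55 is √(0.55 × 0.45/22) = 0.106. The shifts in steps 2 and 3 are smaller than that; the one in step 5 is about three times as large.

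**The case against.** Several stronger readings are tempting, and the documents do not support them.

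- **That the curve ends at zero.** This follows only if the title of Table 92 overrides SAP 2.4.7. The section text names the As-Treated population, and its censoring rules make sense only if patients without recurrence are included. It is a conflict between title and text, not an established restriction.
- **That every recurrence is dated late.** CT, CA-125 and the removal-planned field are recorded at the same visits. If removal is planned at the visit where both criteria are met, there is no delay against the protocol's own definition. The CA-125 values need be only a week apart, and Listing 29 foresees unscheduled visits. Three months is one nominal interval, a worst case.
- **That censoring at removal biases the curve.** Step 3 shows bias only if removal is linked to recurrence risk. For patients who withdraw, the device comes out before exit and no later data exist, so censoring at or about removal is right.
- **That the curve is biased overall, or spoils a comparison with published progression-free survival.** Late dating raises the curve and a recurrent-only set lowers it, so the net direction is unknown. Neither document plans to set the curve beside the 12 to 21 months quoted in Protocol 1.1.
- **That the event should be either criterion, or death.** That would replace the plan's two-part definition with a different and debatable endpoint.

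All of this stands, as does the fact that the curve is a descriptive item under Device Removal and neither a primary nor a secondary endpoint. What it does not answer is that post-removal assessments are collected and then ignored, and that progression without a removal reason cannot be an event. A link between removal and risk is also not far-fetched. Local cancer progression at the suture sites is among the adverse events leading to removal in Protocol 4.1.1. If coded as an adverse-event removal and not as progression or other, it would be censored as recurrence-free.

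**Conclusion.** The point holds in a limited form. As defined, the curve estimates time to planned removal. It can run late by 0 to about 3 months, it omits recurrences without removal or after an earlier one, and it can be biased when removal depends on risk. At the middle assumption the first effect is worth 0 to 0.09 on the 12-month share. Censoring at removal is worth −0.041 to +0.033 on the 18-month share when the hazard is halved or doubled and 5% to 30% of patients are affected. The number of omitted recurrences cannot be sized from the documents. The title conflict would have by far the largest effect (about 0.24 against 0.55 at 12 months), but only if the title is followed. The silence on death alone would be a missing detail; it belongs in the same correction.

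These sizes rest on exponential recurrence and on assumed lags, removal shares and hazards. The primary safety test is unaffected. Severity is low to moderate.

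**What to change.** 1. **SAP 2.5.** In all As-Treated patients, date recurrence at the first visit where the protocol's existing definition, RECIST 1.1 and CA-125 together, is documented, whatever the removal status. The visit-level CA-125 progression and Objective Subject Response fields in SAP 2.4.4 already supply this.
2. **SAP 2.4.7.** Censor recurrence-free patients at their last disease assessment, not at removal. For withdrawn patients this falls at or about removal. The same rule covers patients who reach 18 months without recurrence, for whom no rule is now given.
3. **Death.** State how death without recurrence is handled: competing event, event or censoring.
4. **Consistency.** State how patients placed in the recurrent group through an other removal reason are counted and dated if the two-part definition is not documented, and whether the 180-day platinum split uses the new date.
5. **Table 92.** Retitle it as time to recurrence in As-Treated patients. Tables 88 and 89 already report time to removal.

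None of this touches when or why a device is removed. The cost is minor SAP wording and programming, with no new data. The one downside is that the curve may count recurrences that the removal-based recurrent group does not, so a sentence should explain the difference.

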2.5. Derived Criteria Calculation

If at least one of the items needed to calculate a derived criterion is missing then the corresponding derived criterion will be considered as missing.

- Derived criterion “ITT population” will be defined as follows:

If “Signed Informed Consent” = “Yes” and the date of signature of the consent form is filled and all inclusion/exclusion criteria are compliant and “Can the patient be treated with M-Trap” = “Yes” then “ITT population” = “YES”, else “ITT population” = “NO”.

- Derived criterion “As-Treated population” will be defined as follows:

If the date of signature of the consent form is filled and are compliant with all inclusion/exclusion criteria and “Can the patient be treated with M-Trap” = “Yes” and at least one device successfully implanted then “As-Treated population” = “YES”, else “As-Treated population” = “NO”.

- Derived criterion “Age at Enrollment” will be calculated as follows:

“Age at Enrollment” = “Date of signature of Informed Consent” – “Birth date” in years

- Derived criterion “Duration of patients Follow-up” will be calculated as follows:

“Duration of patients Follow-up” = “Last patient follow-up date” – “Procedure patient date”

If patient procedure date is missing Baseline/Screening date will be used (for ITT population)

- Derived criterion “Duration debulking surgery” will be calculated as follows:

“Duration debulking surgery” = “end time of debulking surgery” – “start time of debulking surgery”

- Derived criterion “Duration of implantation” will be calculated as follows:

“Duration of implantation” = “end time of implantation” – “start time of implantation”

- Derived criterion “Total number of procedures” will be equal to the number of checked boxes for “Extensive upper abdominal” and “Other procedures”.

- Derived criterion “Total number of extensive procedures” will be equal to the number of checked boxes for “Extensive upper abdominal”.

CRO will send to MTrap an Excel file with the list of all other surgical procedures to count their number.

- Derived criterion “Number of extended procedures (Patankar definition)” will be calculated as follows:

All patients start with a score of 1, since all patients had cytoreduction surgery.

Add 1 to the score if Pelvic or Para-aortic or Inguinal lymph node dissection are ticked or if any other procedure includes lymph node dissection (lymphadenectomy).

STATISTICAL ANALYSIS PLAN

Add 1 to the score if Small bowel resection is ticked.

Add 1 to the score if Large bowel resection is ticked (colectomy, rectosigmoid resection).

Add 1 to the score if Diaphragm peritonectomy or Full-thickness diaphragm resection (diaphragm resection) is ticked.

Add 1 to the score if Partial hepatectomy (hepatic resection) is ticked.

- Derived criterion “freedom of device- and procedure-related major adverse events through 6 months post-implantation, including shock, cardiac arrest, myocardial infarction, pulmonary embolism, prolonged intubation, unplanned reintubation, or adverse events leading to removal of the device, including infection, seroma formation, mesh migration, bowel obstruction, adhesions, and local cancer progression through the abdominal wall at M-Trap suture sites” which is the primary endpoint will be calculated as follows:

If a MAE occurred in a patient within 6 months \pm 2W post implantation and “Does this event meet the definition of a major adverse event for the primary endpoint?” = “Yes” then “freedom of device- and procedure-related major adverse events through 6-months post-implantation” = “No” else “freedom of device- and procedure-related major adverse events through 6-months post-implantation” = “Yes”.

- Derived criterion “recurrent patients” will be defined as patients with device removal reason “Disease progression as defined by objective RECIST 1.1 and CA-125 criteria” or device removal reason “other” that indicates recurrence. Derived criteria “non-recurrent patients” are the remaining patients. CRO will send to MTrap an excel file with the list of all other reason of device removal to identify the reason that indicates “recurrence”.
- Derived criterion “time to recurrence” will equal to the date of the follow-up visit when “Device removal planned for this visit” is yes minus the procedure date.
- Derived criterion “platinum resistant, recurrent patients” will be defined as “recurrent patients” where the difference between the date of the follow-up visit when “Device removal planned for this visit” is yes and the date of the most recent chemotherapy medication treatment is less than or equal to 180 days.
- CRO will send to MTrap an excel file with the list of the concomitant medication to identify the chemotherapy medication treatment. Derived criterion “platinum sensitive, recurrent patients” will be defined as “recurrent patients” that are not “platinum resistant, recurrent patients”.
- Histopathologic evidence of tumor cell capture is “Yes” if Tumor cell infiltration for at least one device is >0 in a patient. Otherwise, Histopathological evidence of tumor cell capture is “No”.
- An AE will be considered as an SAE if “Serious Adverse event” = “Yes”.
- An AE will be considered “Unanticipated” if “Anticipated adverse event” = “No”.
- An AE will be considered as device related if “Relationship to device(s)” is “possible”, “probable” or “definite”.
- An AE will be considered as procedure related if “Relationship to procedure” is “possible”, “probable” or “definite”.
- At least one other medical history will be calculated as follows:

If at least one variable of other medical history is equal to “Yes” then “At least one other medical history” = “Yes”,

If no variable of other medical history is equal to “Yes” then:

- If all variables of other medical history are equal to “No” then “At least one other medical history” = “No”,
- If at least one variable of other medical history is equal to “Missing” then “At least one other medical history” = “Missing”,

If all variables of other medical history are equal to “Missing” then “At least one other medical history” = “Missing”.

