## **4.1. Primary Endpoint(s)**

### **4.1.1. Primary Safety Endpoint(s)**

The primary safety endpoint is incidence of device- and procedure-related major adverse events, defined as severe complications based on Clavian Class IV complications, through 6-months post-implantation, including shock, cardiac arrest, myocardial infarction, pulmonary embolism, prolonged intubation, unplanned reintubation, or adverse events leading to removal of the device, including infection, seroma formation, mesh migration, bowel obstruction, adhesions, and local cancer progression through the abdominal wall at M-Trap suture sites.

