A medical coding will be done on the adverse events using the MedDRA dictionary. All adverse events (AEs) will be categorized by system organ class (SOC) and preferred term (PT). A complete description will be done: total number of AEs, device related AEs, serious AEs, device deficiencies, SAEs, USADEs, and number of subjects with at least one of the respective categories: AEs, SAEs, etc. The causality relationship will be presented for all AEs.

Data will be locked and summarized for each DSMB meeting. An interim analysis will be performed after all patients reach the 6-month time point to support the CE-marking application.

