1.3. Study Plan

1.3.1. Patient's Follow-up

Nine (9) visits are scheduled:

- Visit 0: Screening within 21 days
- Visit 1: Procedure (D0)
- Visit 2: 1 Month (± 1 week)
- Visit 3: 3 Months (± 2 weeks)
- Visit 4: 6 Months (± 2 weeks)
- Visit 5: 9 Months (± 1 month)
- Visit 6: 12 Months (± 1 month)
- Visit 7: 15 Months (± 1 month)
- Visit 8: 18 Months (± 1 month)

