2. STATISTICAL METHODS

2.1. General Statistical Considerations

2.1.1. Time Points Definition

Baseline/Screening data is defined as the last available observation recorded before the first study device implantation for the patient.

Visit(n) data is defined as the last available observation on or before the Visit(n) time point following the first study device implantation for the patient.

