2.4.5. Primary Analysis

Primary analysis of safety will be performed on the ITT population and the As-Treated populations.

The primary safety endpoint is freedom from device and procedure-related major adverse events through 6-months post-implantation, including shock, cardiac arrest, myocardial infarction, pulmonary embolism, prolonged intubation, unplanned reintubation, or adverse events leading to removal of the device, including infection, seroma formation, mesh migration, bowel obstruction, adhesions, and local cancer progression through the abdominal wall at M-Trap suture sites.

The primary safety endpoint will be analyzed using a unilateral one sample test for binomial proportion at the 5% level. In addition, the exact bilateral 95% confidence interval will also be given. The statistical test for the primary safety endpoint is given by:

- H0: M-Trap freedom MAE incidence \leq 90% - Non-inferiority margin (25%)
- Versus
- HA: M-Trap freedom MAE incidence $>$ 90% - Non-inferiority margin (25%)

A modified primary analysis will also be performed that uses a freedom from MAE incidence rate that is adjusted for the surgical complexity of the study population, as compared to the Patankar study population, which is the basis of the statistical rationale for this study (repeated in the table below). The total number of extended procedures will be split in four classes: 0, 1, 2, 3 and more.

Procedures	0	1	2	3 or more	AVG
Total patients	1352	1214	254	50	2870
Severe complications, n	51	92	44	9	196
Severe complications, %	3.8%	7.6%	17.3%	18.0%	6.8%

A further modified primary analysis will also be performed that only includes procedure-related events through 30 days, as this is the comparable population to the Patankar study population, which is the basis of the statistical rationale for this study.

Primary analysis of performance will be performed on the As-Treated population and by device location. This analysis will be also performed using these 3 following sub-populations: (1) platinum resistant, recurrent patients; (2) platinum sensitive, recurrent patients; (3) non-recurrent patients (see definition in part 2.5).

The primary performance endpoint is histopathologic evidence of tumor cell capture (see 2.5). Histopathology will be performed after device explant.

The primary performance endpoint will be assessed with exact one-sided 90% confidence intervals.

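### SAP 2.5 applies the ±2-week Visit 4 window to the primary safety event cut-off, although the endpoint is defined as through 6 months with no tolerance

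*SAP*

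**What the plan says.** Protocol 4.1.1 sets the period of the primary safety endpoint as "through 6-months post-implantation, including shock, cardiac arrest, myocardial infarction", followed by the rest of the event list. SAP 2.4.5 restates it as "freedom from device and procedure-related major adverse events through 6-months post-implantation". Neither gives a tolerance.

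The operative rule is in SAP 2.5. A patient fails when two conditions hold:

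- The timing condition: she had an MAE "within 6 months \pm 2W post implantation".
- The case report form question "Does this event meet the definition of a major adverse event for the primary endpoint" is answered yes.

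Otherwise she is scored as free of MAEs. The name of the derived variable in the same paragraph still says through 6 months.

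The tolerance equals the visit window in SAP 1.3.1: "Visit 4: 6 Months (± 2 weeks". On timing, Protocol 10.3 says "An interim analysis will be performed after all patients reach the 6-month time point to support the CE-marking application", and SAP 2.1.5 says the same.

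**The concern.** A visit window allows for appointments that cannot all fall on one day. An adverse event has a date of onset, which Protocol 8.4 requires to be recorded, so it can be placed against a fixed limit without a tolerance. With ±2W attached, the SAP does not say whether the limit is 6 months, 6 months plus two weeks, or the date of the patient's own Visit 4.

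This is the primary endpoint of a non-blinded single-arm study. If the limit is not fixed in advance, someone has to choose it while programming, possibly with the events in view. The sample is small enough that reclassifying one patient can turn a pass into a fail. The computed result may also not match the endpoint that the protocol defines.

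**Working it through.** **1. The passages side by side**

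| Place | Limit |
|---|---|
| Protocol synopsis, 4, 4.1.1, 10.1 | through 6 months |
| SAP 1.1, 2.2, 2.4.5 | through 6 months |
| SAP 2.4.5, modified 30-day analysis | 30 days, no tolerance |
| SAP 1.3.1, Visit 4 | 6 months ± 2 weeks |
| SAP 2.5, derivation of the endpoint | 6 months ± 2 weeks |

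Two other rules might settle the matter, but do not. The case report form question has no date rule of its own. SAP 2.1.1 says "Visit(n) data is defined as the last available observation on or before the Visit(n) time point", which governs observations at visits and not event onset.

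**2. Which events are affected**

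The documents do not convert months to days. Taking 6 months as 182.6 days (assumption), the window runs from 182.6 − 14 = 168.6 to 182.6 + 14 = 196.6 days, or about 5.5 to 6.5 months.

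- *6.0 to about 6.5 months:* outside the defined endpoint, but counted if the rule is read to its outer limit and the event is flagged. This is a direct conflict.
- *About 5.5 to 6.0 months:* inside the defined endpoint. These events are in doubt only if the minus sign is read as allowing an earlier limit, for example at an early Visit 4.

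Read literally as an interval, the rule would count only events inside the window, which cannot be intended.

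**3. The plan's own figure**

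Inputs from Protocol 10.1 and SAP 2.2: expected MAE-free rate 0.90, margin 0.25, so null 0.90 − 0.25 = 0.65; one-sided alpha 0.05; n=20. With X binomial(20, p):

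- P(X ≥ 17 | p=0.65) = 0.0444, so 17 of 20 passes.
- P(X ≥ 16 | p=0.65) = 0.118, so 16 of 20 fails.
- P(X ≥ 17 | p=0.90) = 0.867, which agrees with the stated power above 85%.

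At most 3 patients with an MAE are allowed. With 22 analysed the exact limit is also 3 (p=0.0245 with 3, 0.0716 with 4). One patient can therefore decide the test.

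**4. How often the cut-off would change the verdict**

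Every patient with an MAE by 6 months also has one by 6 months plus two weeks. The share of trials in which the verdict changes is therefore the difference between the two pass probabilities.

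*Even spread of 10% over 26 weeks (assumption):*

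| Cut-off | MAE-free rate | P(X ≥ 17), n=20 |
|---|---|---|
| 6 months − 2W | 1 − 0.10×24/26 = 0.9077 | 0.893 |
| 6 months | 0.9000 | 0.867 |
| 6 months + 2W | 1 − 0.10×28/26 = 0.8923 | 0.838 |

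For the two weeks in direct conflict: 0.867 − 0.838 = 0.029, about 3% of trials.

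*Early events (assumption):* suppose a share e of the 10% falls in the first 30 days and the rest is even over days 30 to 183. The extra probability per patient in two weeks is 0.10×(1−e)×14/153.

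- e = 0.5: 0.0046. The pass probability falls from 0.867 to 0.850, about 1.7%.
- e = 0.8: 0.0018. The pass probability falls from 0.867 to 0.860, about 0.7%.

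**5. Effect of a fixed day**

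Sample size, the limit of 3 MAE patients, alpha (0.0444) and power (0.867) do not change.

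**The case against.** The strongest reply is that this is a drafting slip with little effect. Most of that stands.

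- The endpoint is called through 6 months everywhere else, including in the name of the derived variable. The case report form question also refers back to that definition, so a late MAE is not counted automatically. This limits the problem but does not close it, because the question carries no date rule.
- Reading the rule to its outer limit adds failures, which makes non-inferiority harder to show. That is conservative for a safety endpoint.
- The historical rate rests on 30-day postoperative complications, and several listed events are perioperative. An even spread over 6 months therefore probably overstates late events.

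A reader might also infer stronger points that the documents do not support.

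- *The whole four-week band is undefined.* No text moves the limit earlier than 6 months; only one reading of the minus sign does.
- *The result is at risk in 27% or 14% of trials.* With an even spread, 1 − (1 − 0.10×4/26)^20 = 0.27 and 1 − (1 − 0.10×2/26)^20 = 0.14. These are chances that at least one of 20 patients has an MAE in four or two weeks, not chances that the verdict changes.
- *Device removal concentrates events in this band in primary-debulking patients.* The schedule requires their 6-month visit to follow the last infusion. But an adverse event that leads to removal begins before the removal, so removal timing does not make the band special when events are dated by onset.
- *The 6-month analysis necessarily runs before the event window closes.* The text says after all patients reach 6 months, which is a trigger and not a data cut-off on that day. Serious events must be reported within 24 hours of awareness (Protocol 8.4), and patients are followed through 18 months (Protocol 6.2.3).

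**Conclusion.** The inconsistency is real and in current text. The rule that computes the primary safety endpoint carries a visit tolerance that the endpoint's definition does not have, and nothing else in the documents resolves it. The direct conflict is confined to MAEs with onset from 6.0 to about 6.5 months, and only when such an event is flagged as a primary-endpoint MAE.

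One patient can reverse the result at n=20, but this would seldom happen through these two weeks: in about 3% of trials under an even spread of a 10% MAE rate, and in about 0.7–1.7% if 50–80% of MAEs occur in the first 30 days. Both timing patterns are assumptions, since the documents give none. The design and sample size are unaffected. The point is worth correcting because the primary endpoint should have one limit, set before the 6-month lock, and the correction costs almost nothing.

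**What to change.** In SAP 2.5, delete ± 2W from the primary endpoint rule. Count every qualifying MAE by onset date, from implantation through one fixed day equal to 6 months, the same for all patients and regardless of the Visit 4 date. State the conversion; day 183 is one possible choice, but it is not in the documents. Keep ± 2W for visit scheduling only.

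In SAP 2.1.5, add that adverse-event status through that day is confirmed before the 6-month lock for patients seen early in the Visit 4 window. This is needed because the rule scores a patient with no recorded event as MAE-free, and the next scheduled visit is at 9 months ± 1 month.

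The protocol's endpoint definition already has no tolerance, so the protocol needs no change. The cost is SAP wording and a short wait or status check for patients seen early.
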